1.4. Prader-Willi Syndrome

Prader-Willi Syndrome (PWS), first described in 1956, is a multifaceted developmental disorder and the most common genetic syndrome associated with obesity (Gunay-Aygun et al., 1997; McAllister and Whittington, 2011). It is caused by the absent expression of paternally-inherited genes in the PWS region on 15q11-q13 (Ledbetter et al., 1981). While it presents with generalized hypotonia and developmental delay in infancy, PWS then manifests with uncontrollable appetite, hyperphagia, and excessive weight gain leading to severe obesity (Grechi et al., 2012).

Clinically, PWS patients suffer a complex pattern of physical, behavioral, endocrine, and intellectual deficiencies. Endocrine abnormalities lead to hypogonadism and short stature. In particular, growth hormone deficiency is reported to occur in 40% to 100% of the population (Griggs et al., 2015) and is commonly treated with growth hormone (Angulo et al., 2015). Behavioral disorders include obsessive compulsive behaviors such as skin picking, hoarding, redoing, and repetitive speech (Griggs et al., 2015).

However, it is the appetite behavior classified as hyperphagia in Prader-Willi Syndrome that is the most life threatening (Dykens et al., 2007; Griggs et al., 2015) and until recently, no patient lived over the age of 50 due to morbid obesity and its related complications (Aycan et al., 2014). The mortality rate in patients with PWS is six times higher than patients with other intellectual disabilities (Einfeld and Kavanagh, 2006) and mortality in patients not treated with growth hormone was estimated to be 3% per year between the ages of 6 and 56 compared to the general population mortality of 0.13% below 55 years. Mortality in Prader-Willi Syndrome below 5 years of age has not been determined (Eiholzer, 2005).

Hyperphagic behaviors can also be dangerous in persons who are not obese, with increased risks of death due to choking while sneaking food, and gastric perforations after consuming more food than usual (Dykens et al., 2007). Approximately 8% of deaths in individuals with PWS are reported due to the choking, especially on hot dogs (Stevenson et al., 2007). PWS patients also are known to eat discarded (contaminated) food and items that are not for human consumption such as pet food, or even non-food items such as paint or paper (Griggs et al., 2015).

Currently, there are no FDA-approved therapies for the treatment of hyperphagia or obesity in patients with PWS. In addition, drugs that have demonstrated efficacy in the past have been withdrawn or have significant safety concerns (e.g., rimonabant, beloranib). Therapy consists mostly of strict and consistent behavioral controls surrounding eating that prevent independent living for adult patients. Recent studies investigating modulation of the endocannabinoid system, however, have shown promise.

The endocannabinoid system appears to be critically involved in the regulation of appetite, body weight, metabolism, hypothalamic-pituitary-adrenal axis, and reward brain circuitry (Liu et al.,

2005; Edwards and Abizaid, 2016). Endocannabinoid receptor CB1, is widely expressed in the central nervous system, autonomic gastric vagus nerve endings of the peripheral nervous system, and other key cells involved in body energy metabolism, including adipocytes, hepatocytes, and myocytes (Bensaid et al., 2003; Liu et al., 2005; Osei-Hyiaman et al., 2008). In clinical studies, compounds with endocannabinoid effects (fenfluramine, rimonabant) have shown significant effects on weight and appetite suppression (Pinder et al., 1975; Despres et al., 2005; Pi-Sunyer et al., 2006). These effects on appetite also occurred in 19% of epilepsy patients treated with Epidiolex® (i.e., cannabidiol extracted from the cannabis plant) during an open-access program for patients with pediatric seizure disorder (Devinsky et al., 2016). Because of the well-characterized orexigenic activity of THC (a strong CB1 agonist), the CB1 antagonist, rimonabant, was studied and found to be effective in treating obesity in adults without PWS (Pi-Sunyer et al., 2006). Both fenfluramine and rimonabant were subsequently withdrawn from the market, however, due to unacceptable side effects (McCann et al., 1997).

CBD is a low-affinity antagonist of CB1, but it may also modulate CB1 receptor signaling through its inhibition of the metabolism of the endogenous cannabinoid, anandamide (Ibeas Bih et al., 2015; Laprairie et al., 2015). As for appetite, CBD has been shown to decrease food intake in rats under stressful conditions and reduce *ad lib* intake of high-sugar feed when compared to vehicle-treated controls (Silveira Filho and Tufik, 1981). In addition, CBD has been shown to diminish daily food consumption without affecting daily water intake (Wierucka-Rybak et al., 2014) as well as inhibited hyperphagia induced by CB1 receptor or 5-hydroxytryptamine (5-HT_{1A}) serotonin receptor agonists suggesting a role for CBD as a regulator of food intake. Perhaps just as importantly, CBD decreases cue-induced craving and reduces the reward induced by drugs of abuse by modulating the cholanergic-dopaminergic pathway that may drive such behaviors in PWS patients (Von Deneen et al., 2009; Hurd et al., 2015; Parsons and Hurd, 2015).

Thus, CBD may have potential to address the main medical problems associated with Prader-Willi Syndrome patients leading to obesity and related mortality. Insys Development Company, Inc. (Insys) is manufacturing a pharmaceutical grade synthetic cannabidiol formulation (Cannabidiol Oral Solution) to be advanced into clinical development for the treatment of hyperphagia behaviors and obesity in patients with Prader-Willi Syndrome.

1.5. Dose Selection Rationale

Patients total daily dose will range from 20 mg/kg/day, 30 mg/kg/day, and 40 mg/kg/day. Doses of CBD may be adjusted at the investigator's discretion up to a maximum of 40 mg/kg/day. Doses greater than 40 mg/kg/day are not allowed.

1.6. Summary of Potential Risks and Benefits

As reviewed in Sections 1.2 and 1.3, numerous nonclinical and clinical studies have examined other formulations of CBD. Several areas of potential concern have been identified with the use of CBD, especially in nonclinical studies. These include:

• Competitive binding of CYP proteins (thus, an impact on drug metabolism in the liver). Cannabidiol is metabolized predominantly by CYP3A4 and CYP 2C19. Cannabidiol may inhibit these two isozymes, as well as having small effects on CYP3A5, CYP2D6, CYP1A1, and CYP2C9.

• Potential downregulation of immune responses involving the T, B, T-helper, and T cytotoxic subsets of leukocytes and/or those dependent on IL-2 or IFN-γ.

Based on recent studies of cannabinoid administration in humans, controlled CBD may be safe in humans and animals. While further studies are needed to clarify these reported *in vitro* and *in vivo* side-effects (Braut-Boucher et al., 1986), no infection-related events have been reported in recent studies in the pediatric seizure population.

The inclusion/exclusion criteria, concomitant medication guidelines, and safety monitoring (AEs, clinical laboratory, vital signs, ECG, and physical examination assessments) planned for this study are intended to minimize these potential safety risks.

Criteria for removal of subjects from the study and stopping rules will dictate discontinuation of subject participation should a safety issue arise (see Section 3.3 and Section 3.5, respectively).

The appetite behavior classified as hyperphagia in Prader-Willi Syndrome is the most life threatening (Dykens et al., 2007; Griggs et al., 2015) and until recently, no patient lived over the age of 50 years due to morbid obesity and the related complications (Aycan et al., 2014). The mortality rate in patients with PWS is six times higher than patients with other intellectual disabilities (Einfeld and Kavanagh, 2006) and mortality in patients not treated with growth hormone was estimated to be 3% per year between the ages of 6 and 56 years compared to the general population mortality of 0.13% below 55 years; mortality in Prader-Willi Syndrome below 5 years of age has not been determined (Eiholzer, 2005).

Hyperphagic behaviors can also be dangerous in persons who are not obese, with increased risks of death due to choking while sneaking food, and gastric perforations after consuming more food than usual (Dykens et al., 2007). Approximately 8% of deaths in individuals with PWS was reported due to the choking, especially on hot dogs (Stevenson et al., 2007). Prader-Willi Syndrome patients also are known to eat discarded (contaminated) food and items that are not for human consumption such as pet food, or even non-food items such as paint or paper (Griggs et al., 2015).

Subjects with PWS continue to experience a significant unmet medical need, especially when it comes to hyperphagia behavior and obesity. There are no approved drugs currently to treat these behaviors. Fenfluramine demonstrated significant efficacy in Prader-Willi Syndrome patients but was removed from the market due to cardiac valve concerns. Rimonabant was approved in the EU for obesity and a trial was ongoing in Prader-Willi Syndrome. However, the drug was never approved in the US and removed from the market in the EU due to significant psychiatric side effects. A trial in PWS, while demonstrating a trend for efficacy was terminated early for safety concerns. Currently, Zafgen's product Beloranib demonstrated significant positive effects on weight loss and hyperphagia behavior in patients with Prader-Willi syndrome but is currently on hold due to two deaths that were thought to be caused by thrombotic events. Orlistant, locaserin, Qsymia, and Contrave have been approved for obesity but not studied in the Prader-Willi Syndrome population. Therefore, there continues to be a high unmet need for an efficacious and safe treatment for this population.

Cannabidiol has been safely administered to over 300 medically complex children and was generally well-tolerated. The adverse events recorded do not correspond to those encountered by previous trials in patients with Prader-Willi syndrome. The anxiolytic effects of CBD and its indirect effect on the CB1 receptor suggest an improved side effect profile in this population.

27 Feb 2018

In conclusion, there is both pre-clinical and clinical evidence that affecting the endocannabinoid system with cannabidiols, including cannabidiol, may demonstrate a clinically relevant effect on the hyperphagia behaviors as well as lead to weight loss in patients with Prader-Willi Syndrome. Insys believes that due to the safety and tolerability of cannabidiol demonstrated by the data available in the literature and collected by the sponsor, and the life-threatening obesity in Prader-Willi Syndrome, the demonstration of efficacy and safety of Cannabidiol Oral Solution in this population will be a valuable option to treat these patients.

2. STUDY OBJECTIVE

The objective of this study is to assess the long-term safety and tolerability of Cannabidiol Oral Solution (CBD) in patients with Prader-Willi Syndrome.

Downloaded by PPD

3. INVESTIGATIONAL PLAN

3.1. Overall Study Design

This is a multicenter, open-label study designed to assess long-term safety and tolerability of CBD in patients with Prader-Willi Syndrome. Patients must have completed INS011-16-085 to be eligible.

The investigator will ensure that the patients legal representative [parent(s)/caregiver(s)] will receive a copy of the informed consent form for review and provide full informed consent prior to study participation. Patients may enroll in this long-term safety study (INS011-17-115) after completing INS011-16-085 Visit 10 (Study Completion) to avoid interruption of the investigational product. Patients will have up to 2 weeks to enroll in INS011-17-115.

Patients will receive CBD treatment for approximately 48 weeks. Total daily doses ranging from 20 mg/kg/day to 40 mg/kg/day will be administered with standard meal. If any participant does not enroll within the 2 week window, that patient will not be eligible to enroll into the study.

The study will consist of a Safety Period (48±2 weeks), Taper Period (6±3 days), and a Follow-up Period (30±5 days). Treatment visits will be scheduled monthly for the first 3 months and then quarterly over the remaining 9 months. All patients will complete a Visit 7 (End of Study) or Early Withdrawal Visit regardless of when they stop treatment/complete the study. A Follow-Up telephone call (Visit 9) will occur 30 days after the end of either the End of Study (Visit 7) or Early Withdrawal.

Once the informed consent for INS011-17-115 is provided within the required time frame, the patient will receive a total daily dose ranging from 20mg/kg/day to 40mg/kg/day.

Patients will be dosed approximately every 12 hours with food to help ensure consistent plasma levels are achieved. Patients will be dosed for 48 weeks during which the investigator will assess safety and tolerability.

The study will be terminated upon one of the following:

- The investigational product is successfully approved for marketing in the US.
- Sponsor elects to terminate INS011-17-115.
- The patient has received 48 weeks of treatment.

3.1.1. Safety Assessments

At Visit 1 (Day 1) and each monthly and quarterly visit, the following assessments will be completed:

- Review vital signs, clinical labs, ECG, urinalysis (Visit 1 only), urine preganacy screen, urine drug screen, weight and physical examination.
- Review concomitant medication and adverse events (AEs).
- 12-lead ECG.

- Columbia-Suicide Severity Rating Scale (C-SSRS) will be used for children and adolesents aged 7 to 17 years, if appropriate.
- Dispensing CBD.
- Drug accountability.

At Visit 7 (End of Study) or Early Withdrawal Visits the following assessments will be completed:

- Review vital signs, clinical labs, ECG, urinalysis, urine preganacy screen, urine drug screen, weight and physical examination.
- Review concomitant medication and adverse events (AEs).
- 12-lead ECG.
- Columbia-Suicide Severity Rating Scale (C-SSRS) will be used for children and adolesents aged 7 to 17 years, if appropriate.
- Hyperphagia Questionnaire for Clinical Trial (HQ-CT).
- Dispensing CBD.
- Drug accountability.

All AEs that arise during the Safety, Taper, and Follow-up Periods will be documented.

3.1.2. Taper Period

At the end of the Long-Term Safety study patients will be tapered off of CBD over a 0-6 day period. The following tapering scheme will be utilizied: 40 mg/kg/day will be reduced to 30 mg/kg/day for three days, then 30 mg/kg/day will be reduced to 20 mg/kg/day for three days and then discontinued; 30 mg/kg/day will be reduced to 20 mg/kg/day for three days and then discontinued. This can be modified by the investigator based upon the patient's response

[figure not shown]
Tapering will occur under the following circumstances:

- Patient completes Visit 7 (End of Study). Patient will begin tapering the day after Visit 7.
- Patient withdraws early. Patient will begin tapering the day after the investigatory has been informed of the decision to withdraw from the trial.

3.1.3. Follow-Up Period

A follow-up telephone call (Visit 9) will occur 30 days after the Visit 7 (End of Study) or Early Withdrawal to assess AEs and record concomitant medications.

Figure 1: Study Design Schematic

3.2. Patient Selection

3.2.1. Inclusion Criteria

Patients must meet all of the following inclusion criteria:

- 1. Completed all activities through Visit 10 (Study Completion) of INS011-16-085.
- 2. Patient and/or parent(s)/caregiver(s) fully comprehend the informed consent form (ICF) and assent form, understand all study procedures, and can communicate satisfactorily with the investigator and study coordinator, in accordance with applicable laws, regulations, and local requirements.
- 3. If female, is either not of childbearing potential (defined as premenarchal or surgically sterile [bilateral tubal ligation, bilateral oophorectomy, or hysterectomy]) or practicing one of the following medically acceptable methods of birth control:
 - a. Hormonal methods such as oral, implantable, injectable, vaginal ring, or transdermal contraceptives for a minimum of 1 full cycle (based on the patient's usual menstrual cycle period) before study drug administration.
 - b. Total abstinence from sexual intercourse since the last menses before study drug administration.
 - c. Intrauterine device.
 - d. Double-barrier method (condoms, sponge, or diaphragm with spermicidal jellies or cream).
- 4. Psychotropic treatment will be permitted if the subject has been on a stable dose during the INS011-16-085 and does not anticipate a dose change during the course of the study.
- 5. Growth hormone treatment will be permitted if the subject has been on a stable dose during INS01-16-085.
- 6. Any other treatment including thyroid hormones should be stable prior to entering the INS011-17-115 study.
- 7. In the opinion of the investigator, the parent(s)/caregiver(s) is (are) willing and able to comply with the study procedures and visit schedules, including venipuncture, and the visit schedules.

3.2.2. Exclusion Criteria

Patients will be excluded for any of the following:

- 1. Patient or parent(s)/caregiver(s) have daily commitments during the study duration that would interfere with attending all study visits.
- 2. Experienced an anoxic episode related to study drug requiring resuscitation during their previous study.
- 3. Uncontrolled Type I and Type II diabetes.

- 4. Developed an adverse event thought to be related to CBD in the previous study and for whom the Investigator determines that continuing treatment with CBD would not be in the best interest of the patient.
- 5. History of clinically significant gastrointestinal, renal, hepatic, neurologic, hematologic, endocrine, oncologic, pulmonary, immunologic, psychiatric, or cardiovascular disease, or other condition which would jeopardize safety or impact validity of results (per investigator).
- 6. Currently taking felbamate.
- 7. Compromised respiratory function or severe respiratory insufficiency.
- 8. Pregnant or lactating female.
- 9. In the opinion of the investigator, the patient is unsuitable in any other way to participate in this study.

3.3. Removal of Patients from Therapy or Assessment

Patients will be allowed to discontinue their participation in the study at any time for any reason (withdrawal of consent). Furthermore, participation in this clinical study may be discontinued by the Investigator or by the sponsor for any of the following reasons:

- Intolerable side effects of the study product.
- Changes in medical status or medical condition of the patient such that the Investigator believes that patient safety will be compromised or that it would be in the best interest of the patient to stop treatment.
- Pregnancy.
- Relevant non-compliance with the protocol.
- Any use of marijuana, confirmed by a positive drug screen for THC.

In the event of a patient's withdrawal, the Investigator will promptly notify the sponsor. Every effort will be made to complete the end-of-study assessments.

Should any patient choose to withdraw early from the study, they will be advised of the safety precautions to be taken and will be followed until resolution of any AE or until the unresolved AEs are judged by the investigator to have stabilized.

3.4. Dose Adjustment Criteria

Patients may have their dose of study medication adjusted down once from 40 mg/kg/day to 30 mg/kg/day or 30 mg/kg/day to 20 mg/kg/day at the discretion of the Investigator or qualified designee based on the patient's tolerability. If the lower dose is not tolerated, the drug will be discontinued and the patient will be withdrawn from the study.

All dose changes must be clearly documented in the eCRF.

3.5. Stopping Rules

The Investigator reserves the right to terminate the study in the interest of patient safety and welfare. The Sponsor reserves the right to terminate the study at any time for administrative reasons. Patients will also be discontinued when their liver enzymes and serum bilirubin reach:

- ALT or AST $> 8 \times ULN$.
- ALT or AST > 5 x ULN for more than 2 weeks.
- ALT or AST > 3 x ULN and (TU>2 x ULN or INR>1.5).
- ALT or AST > 3 x ULN with appearance of fatigue, nausea, vomiting, right upper quadrant pain or tenderness, fever, rash, and/or eosinophilia (> 5%).

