Review of inclusion/exclusion criteria **	X				>		
C-SSRS	X			X	X		
Review concomitant medications	X	X	Х	х	X	X	X
Vital signs ^b	X	X	X	X	X		
Clinical labs ^c	X	X	X	X	X		
12-lead ECG	X	X	X	X	X		
Urinalysis	X	7		X	X		
Urine pregnancy screen for post-menarchal females	X		> >	X X			
Urine drug screen	X			X	X		
Physical examination ^d	X	X	X	X	X		
Hyperphagia Questionnaire for Clinical Trial (HQ-CT)				X	X		
Dosing with Cannabidiol Oral Solution	X	X	X	X	Xe	X e	
Drug accountability	X	X	X	X	X	X	
AEs	X	X	X	X	X	X	X

ASSESSMENTS	SAFETY PERIOD					TAPER PERIOD	FOLLOW-UP PERIOD ^g
Visit Number 1 ^a		2, 3, 4 (monthly)	5, 6 (quarterly)	7 (End of Study)	Early Withdrawal 8		9 (Phone Call)
Study Time Points	Day 1	Weeks 4, 8, 12	Weeks 24, 36	Week 48		0-6 Days	30 Days After EOS
Visit Window (Days)	± 5	± 5	± 5	± 3		± 3	± 5
End of Study				X	X ^f		

^{**} To be completed prior to enrollment into LTS, specifically within the 2-week period that is allotted post completion of Visit 10 (Study Completion) of INS011-16-085.

AE = adverse event.

^a For patients who enroll within the first 2 weeks after completion of Visit 10 (Study Completion) of INS011-16-085 protocol.

^b Vital signs will be taken after a 5-minute seated rest.

^c If the total bilirubin laboratory value is abnormal, direct bilirubin will be drawn.

^d The physical examination will include weight, and evaluation of general appearance, skin, eyes, ears, nose, throat, neck, lymph nodes, chest, heart, abdomen, and extremities.

^e Following the Safety Period or if the patient withdraws early, the patient will enter a Taper Period. Patients will be tapered off of Cannabidiol Oral Solution as follows: 40 mg/kg/day will be reduced to 30 mg/kg/day for three days, then discontinued; 30 mg/kg/day will be reduced to 20 mg/kg/day for three days, then discontinued. This can be modified by the investigator based upon the patient's response.

f If the patient withdraws prematurely from the Safety Period, all Visit 7 (End of Study) procedures should be conducted. Site staff will follow up with the patient 4 weeks after completion of treatment via the telephone to collect information regarding AEs and concomitant medications.

Follow-up Period Visit 9 will be a phone call.

TABLE OF CONTENTS

PROTOC	COL APPROVAL PAGE	2
PROTOC	COL SYNOPSIS	3
TABLE 0	OF CONTENTS	10
List of Ta	ables	14
List of Fi	gures	14
LIST OF	ABBREVIATIONS AND DEFINITIONS OF TERMS	15
1.	INTRODUCTION	18
1.1.	Cannabidiol	18
1.1.1.	Mechanism of Action	19

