4.8. Treatment After the End of Study

After the Safety Period, patients will have their taper schedule initiated over a 3-6 day period (see Section 3.1.2).

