7.2. End of Study (Visit 7) or Early Withdrawal

The following procedures and assessments will be performed:

- Review/assess concomitant medications.
- Record vital signs (seated blood pressure, pulse rate, temperature, and respiration rate).
- Collect blood samples for clinical labs (chemistry and hematology)
- Collect urine sample for urinalysis, urine drug screen, and urine dipstick pregnancy test (all female patients of childbearing potential).
- Perform resting 12-lead ECG.
- Perform physical examinations.
- Record weight.
- Complete the HQ-CT.
- Collect/review CBD.
- Perform drug accountability.
- Review AEs.
- Dispense CBD for Taper Period.

End of Study assessments (If the patient withdraws prematurely from the Safety Period, all Visit 7 (End of Study) procedures should be conducted. Site staff will follow-up with the patient 4 weeks after completion of study via the telephone to collect information regarding AEs and concomitant medications.

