Following the Safety Period or if the patient withdraws early, the patient will enter a Taper Period. Patients will be tapered off of Cannabidiol Oral Solution as follows: 40 mg/kg/day will be reduced to 30 mg/kg/day for three days, then 30 mg/kg/day will be reduced to 20 mg/kg/day for three days, then discontinued; 30 mg/kg/day will be reduced to 20 mg/kg/day for three days, then discontinued. This can be modified by the investigator based upon the patient's response.

fIf the patient withdraws prematurely from the Safety Period, all Visit 7 (End of Study) procedures should be conducted. Site staff will follow up with the patient 4 weeks after completion of treatment via the telephone to collect information regarding AEs and concomitant medications.

Follow-up Period Visit 9 will be a phone call.

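### The liver stopping rule does not say that CBD stops at once, and the early-withdrawal taper has no exemption for it, so on the likeliest reading a patient on 30 or 40 mg/kg/day takes CBD for 3 to 6 more days unless the investigator changes the taper

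*Protocol*

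**What the plan says.** **The rule.** Protocol section 3.5: "Patients will also be discontinued when their liver enzymes and serum bilirubin reach" one of four limits: ALT or AST above 8 x ULN; above 5 x ULN for more than 2 weeks; above 3 x ULN with a second laboratory criterion; or above 3 x ULN with listed symptoms or eosinophilia. The section gives no timing for the last dose and does not mention the taper. Section 1.6 describes the stopping rules as ending the subject's participation.

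**The exit visit.** Section 3.1 gives every patient a Visit 7 or "Early Withdrawal Visit regardless of when they stop treatment/complete the study". Section 3.1.1 lists "Dispensing CBD" among the procedures at that visit, and section 7.2 gives the purpose: "Dispense CBD for Taper Period".

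**The taper.** Protocol Table 1 footnote e: "Following the Safety Period or if the patient withdraws early, the patient will enter a Taper Period". SAP Appendix A carries the same instruction: "if the patient withdraws early, the patient will enter a Taper Period". Under section 3.1.2, a patient on 40 mg/kg/day takes 30 for three days and then 20 for three days; a patient on 30 takes 20 for three days; no step is given for 20. Protocol footnote e has a shorter version from the top dose: "40 mg/kg/day will be reduced to 30 mg/kg/day for three days, then discontinued". Section 4.8 says that after the Safety Period "patients will have their taper schedule initiated over a 3-6 day period", while section 3.1.2 and the schedule tables give 0 to 6 days.

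**Discretion.** The investigator may modify the taper in light of the patient's response (3.1.2) and may direct dose changes (4.6).

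**The concern.** A hepatic stopping rule exists to end exposure. Here the rule says nothing about when exposure ends, while the general exit procedure supplies further drug. A site that follows the schedule would hand CBD to a patient who has just crossed, say, 8 x ULN. Another site could read the same text as an immediate stop. Protection at a liver limit would then depend on how each site reads the text, or on an investigator remembering to override a default. Table 1 schedules no laboratory tests at Visit 8 or Visit 9, so no scheduled liver test covers the taper, although section 6.1.7.8 does require drug-related adverse events to be followed until they resolve or stabilise.

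This is a patient-safety point. It touches no analysis, sample size or endpoint definition.

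**Working it through.** **1. Does a liver stop lead into the taper?**

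- Section 1.6 ties the stopping rules in 3.5 to the end of participation, so a liver stop is an early exit.
- Section 3.1 sends early exits to the Early Withdrawal Visit.
- Sections 3.1.1 and 7.2 dispense CBD at that visit, and 7.2 says it is for the taper.
- Footnote e, in both documents, puts a patient who withdraws early into the Taper Period.
- None of these places excepts a liver stop, and neither document tells a site to stop CBD at once at a liver limit.

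The protocol does not keep withdrawal for the patient's own choice. Section 3.3 lists discontinuations by the investigator or sponsor and then refers to the patient's withdrawal. Section 3.4 has a patient withdrawn for intolerance. Section 9.1.1 lets the sponsor withdraw a patient. A rule-driven exit therefore fits the term.

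**2. Length of the taper.** Counting days in 3.1.2: from 40, 3 + 3 = 6; from 30, 3; from 20, 0. The first two reproduce the 3 to 6 days of section 4.8. Adding the 20 mg/kg/day case gives the 0 to 6 days of section 3.1.2.

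**3. Further CBD if the taper is not modified.** Full-dose days are the total divided by the patient's dose before the taper.

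| Dose at stop (mg/kg/day) | Source | Total (mg/kg) | Days | Full-dose days |
|---|---|---|---|---|
| 40 | 3.1.2; SAP footnote e | 3 x 30 + 3 x 20 = 150 | 6 | 150/40 = 3.75 |
| 40 | Protocol Table 1 footnote e | 3 x 30 = 90 | 3 | 90/40 = 2.25 |
| 30 | 3.1.2; both footnotes | 3 x 20 = 60 | 3 | 60/30 = 2.0 |
| 20 | no taper step | 0 | 0 | 0 |

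The range of 3 to 6 days for patients on 30 or 40 mg/kg/day holds under either version of the taper.

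**4. How many patients?** The documents give no rate of liver stops. Section 1.3 itemises seven early terminations among 52 patients in the sponsor's earlier long-term study in treatment-resistant seizure disorders, and describes none as a liver stop. It does not say whether that study used the same limits. If 0/52 carried over, the one-sided 95% upper limit for the rate is 1 - 0.05^(1/52) = 5.6%. At that rate the expected number among at most 66 patients is 66 x 0.056 = 3.7, about 4. This is an expected count at the upper rate, not a ceiling on the count. It also includes patients on 20 mg/kg/day, who have no taper step. Zero is quite possible.

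**5. What an immediate stop would do to drug levels.** Section 1.3 gives a single-dose half-life of 19.5 to 29.6 h. Assuming linear kinetics, the fraction remaining after time t is 2^-(t/half-life):

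- after 24 h: 42.6% to 57.0%
- after 72 h: 7.7% to 18.5%

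**The case against.** **The wording may already mean an immediate stop.** The taper text uses discontinuation for the point at which CBD ends, and carried into 3.5 that means no more drug. Section 3.4 separates discontinuing the drug from withdrawing the patient. The list of actions for adverse events separates stopping the drug from modifying the dose. The early taper is tied to a decision to withdraw, which the synopsis words as the patient's own. This stands as a reasonable second reading. It does not settle the matter, because section 1.6 treats the stop as an exit and other sections use withdrawal for exits that the patient did not choose.

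**A zero-day taper is allowed.** Section 3.1.2 gives 0 to 6 days and lets the investigator modify the scheme, so omitting the taper would not breach the protocol. That is true, and it limits the risk. But the zero is fully explained by the 20 mg/kg/day patients, who have no step to take, and the discretion is an override tied to patient response rather than to the liver limits. The default remains further dosing.

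**Some supporting text is indirect.** Section 3.1 requires a visit, not a taper, and would let treatment stop before it. Section 7.2 is a list shared with completers. Section 4.8 speaks of the period after the Safety Period. Each is weak alone; the case rests on footnote e, on dispensing at the exit visit and on the absence of any exemption.

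**It is small.** After Week 12, scheduled laboratory tests are 12 weeks (84 days) apart, and 3.75/84 is about 4.5% of one such interval. The figure of 0/52 comes from another population. Both points stand and limit the size of the concern. They do not justify giving more drug once a limit has been met.

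**One sentence in 3.5 might be enough, and a mandatory stop removes discretion.** A specific rule in 3.5 would probably govern. Sites work from the schedule and visit lists, however, and leaving those unchanged would keep a contradiction at the point of dispensing. The documents give no withdrawal-risk data for this population, so the downside of abrupt cessation is uncertain. Even so, the scheme already accepts stopping from 20 mg/kg/day without a taper.

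**Conclusion.** The concern holds and should be fixed. Section 3.5 does not say when CBD stops, and no taper or dispensing text exempts a liver stop. The likeliest reading gives 3 to 6 more days of CBD to a patient on 30 or 40 mg/kg/day, 60 to 150 mg/kg in total, unless the investigator intervenes. This does not mean that the protocol obliges a site to keep dosing: an immediate stop is an open reading, and the investigator has authority to order one.

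Calling the taper reading likeliest is an inference from section 1.6, footnote e and section 7.2, and confidence in it is medium. The dose arithmetic assumes an unmodified taper. The number of patients is not known from the documents; the figure of about 4 of 66 is an expected count that assumes the upper limit from 0/52 applies here.

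**What to change.** State in Protocol section 3.5 that CBD stops immediately, with no Taper Period, when a liver criterion is met. Add an exception for a section 3.5 liver stop to the taper and taper-dispensing text in seven places: the synopsis, sections 3.1.1, 3.1.2, 4.8 and 7.2, Protocol Table 1 footnote e, and SAP Appendix A footnote e.

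The cost is one sentence and seven short phrases, with no extra patients, visits or analyses. The downside is abrupt cessation in the few patients concerned. On the half-life in section 1.3 and assumed linear kinetics, the CBD level would still fall gradually, to about 43-57% after one day and 8-19% after three. That half-life is a single-dose figure from patients with seizure disorders, so the decline is approximate for this population.
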